5.2.4 Post-Surgery: Histopathology Assessment

Lymph node specimens (if taken during surgery) will be evaluated by histopathological analysis along with the breast specimen (lumpectomy or mastectomy) at the conclusion of surgery. If the final pathology indicates that there are positive margins amendable to resection, the patient will be scheduled to undergo re-excision and/or mastectomy in the standard operating room. At the discretion of the treating surgeon, additional re-excisions may be performed for close margins not meeting the definition of a true positive margin.

5.3 Post-Surgery: Adjuvant Radiation Therapy

Patients who require adjuvant radiation therapy postoperatively will be referred to radiation oncologists at the DFCI. If the patient chooses to pursue their radiation treatment with DFCI clinicians (patients are offered a choice as to where to complete their radiation treatment), then the radiation oncologist will be provided with all imaging, including supine MRI images acquired pre-surgery for treatment planning purposes. These images will be utilized for planning of the radiation treatment plan. Following completion of the initial radiation treatment plan, the attending treating radiation oncologists will be asked to complete a brief survey to assess their perceived usefulness of the supine MRI data for treatment planning purposes.

5.4 Duration of Follow Up

All patients will have a post-surgical visit at their surgical institution (BWH or BWFH). Participants will be followed until their first post-surgical visit after the completion of surgical therapy.

5.5 Criteria for Taking a Participant Off-Study

If the patient is enrolled in the study, and they are unable to undergo supine MRI for any reason, or during the course of the supine MRI they are unable to complete the supine MRI series, they will discontinue participation in the study at that time. Those patients who, following enrollment in the trial, do not proceed to receive a pre-surgical MRI, or who do not receive surgery at one of our institutions, will be removed from the study.

Participants will also be removed from study when any of the following criteria apply:

- Lost to follow-up
- Withdrawal of consent for data submission
- Death

The reason for taking a participant off study, and the date the participant was removed, must be documented in the case report form (CRF).

For Centralized Subject Registrations, the research team submits a completed Off Treatment/Off Study form to ODQ when a participant comes off study. This form can be found on the ODQ website or obtained from the ODQ registration staff.

For Decentralized Subject Registrations, the research team updates the relevant Off Treatment/Off Study information in OnCore.

6. EXPECTED TOXICITIES, ADVERSE EVENTS, AND DOSING DELAYS/DOSE MODIFICATIONS

Adverse event (AE) monitoring and reporting is a routine part of every clinical trial. There are no interventional agents (drugs or devices) being investigated as part of this protocol, and therefore there are no associated adverse events such as toxicities that would commonly be anticipated in these scenarios. There are also therefore no protocol-specific dose delays or modifications unique to this study to report.

This protocol will utilize gadolinium contrast-enhanced MRI imaging, which is a standard FDA-approved imaging agent, and expected toxicities are therefore included and described here. The use of gadolinium contrast has been associated with relatively minimal risk compared to other contrast agents; however, some contrast-related reactions have been identified [56, 57]. IV-administered gadolinium contrast has been associated with renal failure and allergic reactions. Both of these events are identified as potential adverse events, and patients will be informed of the risk of such adverse events. Patients that have a known contrast allergy will be excluded from participating in this study. There is approximately 0.07% risk of an allergic reaction with IV contrast according to a retrospective review of 78,353 cases of IV-gadolinium injections published in 2007, with a more recent study reporting an overall adverse effect rate of 0.0404% among 158,439 administrations, within the 0.0003-1.2% range reported in other studies [56, 57]. If an allergic reaction does occur, the procedure will be aborted and supportive care, including maintaining airway and administration of steroids and epinephrine, will be initiated. This will be reported appropriately as an adverse event. Patients will be screened to ensure they are MRI-eligible and those who are not for any reason, including but not limited to renal failure, will be excluded from participating in this study.

In our protocol, two MRI sequences will be obtained. Of these two sequences, prone and supine, the prone sequence is standard and the supine MRI is investigational. Additional adverse events applicable to this study will therefore be related to performance of supine MRI sequences. All patients undergoing supine MRI will already be receiving a prone MRI. To perform supine MRI, patients will be subjected to physical maneuvering required to position them and their breast(s) in the supine position to obtain the imaging series. It is possible that an adverse event may occur during this maneuvering. These events would be unanticipated, and would be reported according to institution guidelines. An additional smaller dose of gadolinium-based contrast agent may be administered prior to supine MRI, which would result in patients receiving higher contrast doses

than routine breast MRI examination. The risk for nephrotoxicity and nephrogenic systemic fibrosis is infinitesimally small in patients with normal renal function, however, and the dose and concentration that each patient receives will be calculated such that FDA guidelines for contrast agents are met and such that there will be no significant increased risk of nephrotoxicity compared to that with routine breast MRI with contrast. The additional dose of contrast may, however, slightly increase the risk of gadolinium-based contrast retention. Recent studies have shown that gadolinium-based contrast may persist long after administration (primarily in the brains of patients who are subjected to four or more contrast-based MRI scans), even in patients with normal renal function. The significance of this retention, however, remains uncertain, as it is currently unknown if these gadolinium deposits are harmful or could lead to adverse health effects.

6.1 Adverse Event Characteristics

- **CTCAE term (AE description) and grade:** The descriptions and grading scales found in the revised NCI Common Terminology Criteria for Adverse Events (CTCAE) version 4.0 will be utilized for AE reporting. All appropriate treatment areas should have access to a copy of the CTCAE version 4.0. A copy of the CTCAE version 4.0 can be downloaded from the CTEP web site_ http://ctep.cancer.gov/protocolDevelopment/electronic_applications/ctc.htm.
- **For expedited reporting purposes only:**
 - AEs for the agent(s) that are listed above should be reported only if the adverse event varies in nature, intensity or frequency from the expected toxicity information which is provided.
- **Attribution** of the AE:
 - Definite – The AE *is clearly related* to the study treatment.
 - Probable – The AE *is likely related* to the study treatment.
 - Possible – The AE *may be related* to the study treatment.
 - Unlikely – The AE *is doubtfully related* to the study treatment.
 - Unrelated – The AE *is clearly NOT related* to the study treatment.

6.2 For Expedited Adverse Event Reporting

6.2.1 Investigators **must** report to the Overall PI any serious adverse event (SAE) that occurs after the intervention, or within 30 days of the intervention, on the local institutional SAE form.

6.2.2 DF/HCC Expedited Reporting Guidelines

Investigative sites within DF/HCC will report AEs directly to the DFCI Office for Human Research Studies (OHRS) per the DFCI IRB reporting policy.

6.3 Expedited Reporting to Hospital Risk Management

Participating investigators will report to their local Risk Management office any participant safety reports or sentinel events that require reporting according to institutional policy.

6.4 Routine Adverse Event Reporting

Not Applicable

7. STUDY CALENDAR

Assessment	Prior to upfront surgery or NAT treatment (within 3 months of registration)	Post-NAT Evaluation	Surgery	Post-operatively (within six weeks after surgery)
History and Breast Exam	X	X		X
Vital Signs	X			X
Conventional Mammogram with or without US	X	X		
Staging biopsy	X			
Informed Consent	X			
Prone MRI	X	X		
Supine MRI	X	X		
Second look Ultrasound / Mammography with/without biopsy*	X*			
Radiologist Surveys	X‡	X‡	X‡	
Surgery			X	
Surgeon Surveys				X
Pathology Review				X
Radiation Oncologist Survey				X†

*Second look ultrasound and/or biopsy will only be performed if deemed necessary by the treating team in scenarios in cases in which additional lesions are newly identified during MRI evaluation (this is an ‘optional’ and not ‘mandatory’ portion of the study)

‡ Radiologist surveys will be completed after second-look US performance (pre/post NAT) and/or at time of breast biopsies (pre/post NAT) and/or at time of lesion localization (day of surgery) when supine MRI information is used.

† Only in cases of patients who are referred for postoperative radiation therapy and have a treatment plan made by DFCI radiation oncologists.

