Breast imaging, most commonly breast CT, is used post-operatively for patients requiring adjuvant radiation therapy, in order to identify radiation delivery regimens that will accurately and completely target the desired tissue while minimizing the effect on surrounding structures such as the heart and lungs. Treatment plans are designed on a patient-by-patient basis, and are influenced by a range of factors including breast density, lumpectomy cavity volume, and use of adjuvant chemotherapy, which can delay radiation treatment and contribute to cavity contraction making cavity identification more challenging [35, 36]. Multiple studies have demonstrated limitations in single-modality treatment planning with significant inter-observer variability in delineation of tumor cavities, and multi-modality imaging using a combination of MRI and CT has been suggested as a way of improving target volume definition in patients with difficult to visualize cavities [35, 37-39]. Jacobson et al, for example, found that acquisition of a non-contrast supine MRI during treatment planning sessions provided more detailed visual information than CT in the post-lumpectomy breast, and suggested that the combination of images could improve delineation of target cavities [35]. Nevertheless, debate remains about the ultimate utility of MRI for breast treatment radiation planning, and additional studies evaluating the potential benefits are warranted [39-42].

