8.1 Data Reporting

8.1.1 Method

The trial is collecting limited data variables. The study team will collect, manage, and perform quality checks on the data for this study. The study will utilize a case report form collected after patients complete all study procedures and up to 30 days after their study completion. Surveys from providers will be collected at the completion of a patient's on study procedures. Data will be collected and shared with an outside collaborator for analysis. The data will not be identifiable.

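### The calendar's six-week slot for the radiation oncologist survey conflicts with the Section 5.3 trigger, so surveys for patients given chemotherapy before radiation may be missed

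*Combined protocol and SAP*

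**What the plan says.** All references are to the combined protocol and SAP.

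- **Section 7 (calendar).** The row "Radiation Oncologist Survey X" has a single mark, in the column headed "Post-operatively (within six weeks after surgery". Its footnote restricts who is surveyed: "Only in cases of patients who are referred for postoperative radiation therapy and have a treatment plan made by DFCI radiation oncologists". The footnote does not extend the window.
- **Section 5.3.** The survey follows an event: "Following completion of the initial radiation treatment plan, the attending treating radiation oncologists will be asked to complete a brief survey". No interval from surgery is given.
- **Section 5.4.** "Participants will be followed until their first post-surgical visit after the completion of surgical therapy".
- **Section 8.1.1.** "Surveys from providers will be collected at the completion of a patient's on study procedures". A separate sentence describes "a case report form collected after patients complete all study procedures and up to 30 days after their study completion".
- **Section 2.1.** Among the factors that shape radiation planning it names "use of adjuvant chemotherapy, which can delay radiation treatment and contribute to cavity contraction making cavity identification more challenging".
- **Sections 1.3 and 9.6.** Secondary objective 4 rests on this survey alone. The planned analysis is a frequency table, with no denominator and no rule for late or missing surveys.

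**The concern.** The calendar counts from surgery, while Section 5.3 counts from the radiation plan. The two agree only when the plan is finished within six weeks of surgery. By the protocol's own account, adjuvant chemotherapy can push radiation later, so a coordinator working from the calendar could close the record before there is a plan to ask about.

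Surveys missed in this way would not be a random subset. They would belong to patients whose radiation waited for chemotherapy, and the response table would describe mostly patients planned early. Because Section 9.6 asks only for frequencies of the responses received, a reader of the results could not see that a group was missing.

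**Working it through.** The plan states no figure for this objective: no expected number of surveys, no precision target and no chemotherapy rate. The check is therefore a comparison of the timing rules, followed by an illustration on assumed values.

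**1. The rules side by side**

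| Place | Clock starts at | Limit |
|---|---|---|
| Section 5.3 | completion of the initial radiation plan | none |
| Section 7, survey row | surgery | six weeks |
| Section 5.4 | surgery | first post-surgical visit |
| Section 8.1.1, surveys | not applicable | when on-study procedures are complete |
| Section 8.1.1, case report form | study completion | 30 days |

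The other calendar footnote on surveys, for radiologists, ties each one to an event (second-look ultrasound, biopsy, localization). The radiation oncologist footnote has no such timing.

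**2. Who is exposed**

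Sections 1.1 and 3.1 admit stage I to III patients having upfront surgery, and Section 3.2 does not exclude planned adjuvant chemotherapy. If chemotherapy starts w weeks after surgery and lasts d weeks, a plan made afterwards falls outside the window whenever w + d > 6. The documents give neither value. With w assumed to be 4, any d above 2 is outside; with w = 0, any d above 6. Patients whose systemic treatment came before surgery (NAT) are probably less exposed. That is an inference; the documents do not say so.

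**3. Does another section settle it?**

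Section 8.1.1 comes closest. If the survey counts as an on-study procedure, collection waits for it and nothing is lost. If on-study procedures end with follow-up under Section 5.4, the survey must be in hand by the first post-surgical visit. The text supports either reading.

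**4. Illustration of size**

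Inputs: 73 eligible patients (Section 9.2). Assumed: 50% to 90% have a plan made at DFCI, and 10% to 40% of those receive chemotherapy before radiation.

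- Surveys expected: 73 × 0.5 = 36.5 to 73 × 0.9 = 65.7.
- Outside a strict window: 36.5 × 0.1 = 3.7 to 65.7 × 0.4 = 26.3, or about 4 to 26.
- 95% half-width at 50% rating the images useful, 1.96 × √(0.25/m):
  - m = 65.7 gives 0.121. After losing 10% (m = 59.1) it is 0.127; after losing 40% (m = 39.4), 0.156.
  - m = 36.5 gives 0.162. After losing 10% (m = 32.9) it is 0.171; after losing 40% (m = 21.9), 0.209.
- Shift in the reported proportion = share missed × difference in response between the groups. For a 20-point difference: 0.1 × 0.20 = 0.02 to 0.4 × 0.20 = 0.08.
- Sign, with 30% missed and 50% useful among early-planned patients:
  - 80% useful among delayed patients: 0.7 × 0.5 + 0.3 × 0.8 = 0.59 for all patients, against 0.50 reported.
  - 20% useful among delayed patients: 0.7 × 0.5 + 0.3 × 0.2 = 0.41 for all patients, against 0.50 reported.

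**The case against.** The best defence is that the calendar is coarse and the text governs. The six-week column is the only one after surgery, so every post-operative item had to go there. The surgeon survey sits in it too, although Sections 5.1 and 5.2.3 tie that survey to the end of the operation. Section 5.3 sets no deadline, the footnote presupposes that a plan exists, and the off-study criteria in Section 5.5 contain no six-week rule. The respondent is a clinician, so the end of patient follow-up need not stop the survey. All of this stands, and it means the plan can be carried out without loss. It does not remove the conflict, because two coordinators could follow different sections in good faith.

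A reader might infer that data close 30 days after study completion and so shut out late surveys. The documents do not support that. The 30-day clause in Section 8.1.1 governs the case report form, and provider surveys have their own sentence without that limit. Section 8.1.2 sets 30 days from coming off study for data forms and does not name surveys.

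A reader might also infer from Section 2.1 that the missing patients are those in whom the images help most. That paragraph concerns finding the post-operative cavity, and the supine MRI study it describes acquired images at treatment planning. This trial supplies images taken before surgery, which cannot show the cavity. The protocol therefore does not link delay by chemotherapy to the usefulness of these images in either direction.

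Finally, the objective is exploratory and descriptive, and its respondents are already selected, since Section 5.3 lets patients choose where to have radiation. Both points limit the weight of the concern.

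**Conclusion.** The timing conflict is on the page. Section 7, with Sections 5.4 and 8.1.1, can be read to end survey collection before the event that triggers the survey in Section 5.3. Applied literally, the calendar would selectively miss patients who have chemotherapy before radiation, probably mainly in the upfront-surgery group.

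It would go too far to say that these patients are systematically lost or that the reported usefulness is biased. No section refuses a late survey, and the documents give no chemotherapy rate, treatment duration or survey response rate. The conclusion is that surveys may be missed, with size and direction unknown. The range of 4 to 26 surveys, and the shifts shown with it, rest wholly on assumed values. The consequence is confined to secondary objective 4. It is worth correcting because the survey is that objective's only measure and the correction is cheap.

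**What to change.** - **Sections 5.3 and 7:** keep the Section 5.3 trigger and amend the calendar footnote so that the survey is due when the initial radiation plan is completed, whenever that occurs.
- **Sections 5.4 and 8.1.1:** state that the end of patient follow-up does not end survey collection, and that this survey may be collected after the patient's last study visit.
- **Section 9.6:** report the number of surveys expected (patients with a plan made at DFCI) and received, by adjuvant chemotherapy status (yes/no). This requires chemotherapy status to be recorded for those patients.

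Cost: wording changes and one recorded item, with no added patient visit or procedure. Some surveys will arrive months later, which delays closing this one descriptive table.

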8. DATA REPORTING / REGULATORY REQUIREMENTS

Adverse event information and instructions for AE reporting can be found in Section 6 (Adverse Events: List and Reporting Requirements).

8.1 Data Reporting

8.1.1 Method

The trial is collecting limited data variables. The study team will collect, manage, and perform quality checks on the data for this study. The study will utilize a case report form collected after patients complete all study procedures and up to 30 days after their study completion. Surveys from providers will be collected at the completion of a patient's on study procedures. Data will be collected and shared with an outside collaborator for analysis. The data will not be identifiable.

8.1.2 Responsibility for Data Submission

Investigative sites within DF/HCC are responsible for submitting data forms to the Overall PI within 30 days of a patient coming off study.

8.2 Data Safety Monitoring

The DF/HCC Data and Safety Monitoring Committee (DSMC) will review and monitor toxicity and accrual data from this study. The committee is composed of clinical specialists with experience in oncology and who have no direct relationship with the study. Information that raises any questions about participant safety will be addressed with the Overall PI and study team.

The DSMC will review each protocol up to four times a year or more often if required to review toxicity and accrual data. Information to be provided to the committee may include: up-to-date participant accrual; all grade 2 or higher unexpected adverse events that have been reported; summary of all deaths occurring with 30 days of intervention for Phase I or II protocols; any response information; audit results, and a summary provided by the study team. Other information (e.g. scans, laboratory values) will be provided upon request.

8.3 Multicenter Guidelines

Not applicable

8.4 Collaborative Agreements Language

Not applicable

9. STATISTICAL CONSIDERATIONS

This is a phase II study aimed at evaluating the ability of breast MRI (prone and supine) to accurately estimate breast tumor size (in term of correlation with gold standard size on post-operative pathology analysis). This study is also designed to compare correlation between supine

breast MRI with existing imaging modalities at estimating tumor size. Finally, this study is designed to characterize the changes occurring in breast tumor-associated properties/dimensions between the prone and supine imaging position and to determine the correlation of tumor location and geometry on pre-surgical supine MRI and prone MRI. A total of 80 patients will be recruited to participate in this study.

9.1 Study Design/Endpoints

The primary objective of the study is to determine the usefulness of pre-surgical prone and supine MRI for estimating tumor size (as compared to tumor size on post-operative pathology, which is the existing gold standard). This will be evaluated using correlation coefficients between estimated tumor size on prone MRI and estimated tumor size on post-operative pathology.

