1.2 Primary Objectives

The primary objectives are:

- 1) Determine the Pearson correlation between pre-operative prone and supine MRI for estimating tumor size as compared to the gold standard of pathologic evaluation of the surgical specimen.
- 2) To compare the Pearson correlation between pre-surgical standard imaging (mammography, ultrasound, prone MRI) and the gold standard of pathologic evaluation of the surgical specimen and the Pearson correlation between pre-surgical supine MRI and gold standard of pathologic evaluation of the surgical specimen for the evaluation of tumor size.
- 3) To explore the potential changes occurring in tumor-associated properties/dimensions between the prone and supine imaging position and to determine the correlation of tumor location and geometry on pre-surgical supine MRI with prone MRI. Tumor location will be assessed in terms of distance from nipple, chest wall, and skin. Tumor geometry will be assessed on multiple properties including volume, surface area, diameter, sphericity, and compactness. Patients with both pre-NAT and pre-surgical MRI will also be evaluated for the pre-NAT prone/supine MRI and pre-surgical prone/supine MRI comparison.

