9.2 Sample Size, Accrual Rate and Study Duration

For the primary outcome, with 73 eligible patients we will have 90% power to detect a correlation coefficient between pre-surgical prone or supine MRI and tumor size of 0.85 from 0.70 with a two-sided one sample z-test at $\alpha=0.05$ level.

With 73 eligible patients, we will also have more than 80% power to detect a difference in correlation from 0.85 between the supine MRI and the pathology tumor size and 0.70 between the standard imaging and the pathology tumor size with a two-sided two sample z-test at $\alpha=0.05$ level, assuming the correlation between the supine MRI and the standard imaging is 0.70.

Assuming the dropout rate will be 10%, we will plan to accrue a total of 80 patients. With an anticipated enrollment of 5 patients per month, accrual should be completed in approximately 16 months.

The below table “Accrual Targets” reflects the accrual targets anticipated for this study. As noted in detail in Section 3.3, men are not likely candidates for breast conserving surgery, and are not eligible for this trial. Approximately 10% of the target enrollment will be Hispanic or African American.

Accrual Targets					
Ethnic Category	Sex/Gender				
	Females	+	Males	=	Total
Hispanic or Latino	8	+	0	=	8
Not Hispanic or Latino	72	+	0	=	72
Ethnic Category: Total of all subjects	80 (A1)	+	0 (B1)	=	80 (C1)
Racial Category					
American Indian or Alaskan Native	1	+	0	=	1
Asian	4	+	0	=	4
Black or African American	12	+	0	=	12
Native Hawaiian or other Pacific Islander	0	+	0	=	
White	63	+	0	=	63
Racial Category: Total of all subjects	80 (A2)	+	0 (B2)	=	80 (C2)

(A1 = A2)

(B1 = B2)

(C1 = C2)

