9.5 Analysis of Primary Endpoints

There are three primary objectives of this study, each with unique endpoints.

The first is to evaluate the correlation between prone breast MRI and pathologic measurement in estimating tumor size, and the correlation between supine breast MRI and pathologic results. A 95% confidence interval will also be calculated for each correlation coefficient. One sample z-test will be conducted to compare whether these correlation coefficients are different from 0.6.

The second is to compare the correlation between supine breast MRI and pathologic measurement for estimation of tumor size, and the correlation between existing breast imaging modalities and pathologic tumor size. Similarly, correlation coefficient will be calculated between supine MRI and the pathologic results and between existing breast imaging modalities and the pathologic tumor size. Two-sample z-test for comparing correlated correlation coefficients will be conducted to compare whether these two correlation coefficients are equal.

The third is to characterize the changes occurring in breast tumor-associated properties/ dimensions between the prone and supine imaging position for all patients with pre-surgical MRIs. We will also determine the correlation of tumor location and geometry on pre-NAT and post-NAT (pre-surgical) supine MRI with prone MRI among the subgroup of patients with pre and post NAT imaging. As described in Section 2.1, in our prior work comparing prone to supine MRI, we utilized image processing software that enabled us to generate tumor models and specifically calculate differences in the metrics computed from the segmented tumor label maps on supine and prone MRI. As a first order statistics, we plan to examine differences in the shape

and size of the tumor on supine and prone MRI. Further, we hope to correlate these difference metrics with variables including but not limited to breast size (measured on the axial slice through the nipple) and location (inner/outer, upper/lower). Correlation coefficients will be calculated for parameters related to tumor shape and size between supine and prone MRI, and one sample t-test (or non-parametric Wilcoxon test) will be used to test whether the difference in shape and size parameters between these two measurements are significantly different from 0. A regression model will be used to check whether these differences are correlated to breast size and location, age and other clinical characteristics.

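### No rule says whether the prone test, the supine test, either or both decide the first primary objective, and 9.1 evaluates it with prone MRI alone

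*Combined protocol and SAP*

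**What the plan says.** Four places in the combined protocol and SAP describe the first primary objective.

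- **1.2, objective 1** covers both scans: "Determine the Pearson correlation between pre-operative prone and supine MRI for estimating tumor size", with pathology as the reference.
- **9.1** opens with both scans: "The primary objective of the study is to determine the usefulness of pre-surgical prone and supine MRI for estimating tumor size". The next sentence, which defines the evaluation, names one: "This will be evaluated using correlation coefficients between estimated tumor size on prone MRI and estimated tumor size on post-operative pathology".
- **9.2** claims 90% power from 73 evaluable women, using a one-sample z-test, two-sided at 0.05. The effect it is meant to detect is given as "a correlation coefficient between pre-surgical prone or supine MRI and tumor size of 0.85 from 0.70".
- **9.5** computes a correlation with pathology for each scan, with a 95% confidence interval, and adds: "One sample z-test will be conducted to compare whether these correlation coefficients are different from". The null value stated there is 0.6.

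Section 9.5 also states: "There are three primary objectives of this study, each with unique endpoints". The second objective compares the supine-pathology correlation with that of existing imaging, which 1.2 lists as mammography, ultrasound and prone MRI. No section ranks the objectives, divides alpha, or says which scan must succeed for objective 1.

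**The concern.** Supine MRI is the investigational scan, and 1.1 gives its value as the purpose of the trial. Taken alone, the evaluation sentence in 9.1 measures the first primary objective on the standard scan only. Taken with the wording of 9.2, a significant result on either scan might be counted. Taken with 9.5, two tests are run and nothing says how to combine them.

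These readings lead to different conclusions from the same data. If prone is significant and supine is not, one reading calls objective 1 met and another calls it failed. The choice could then be made after the results are known. The two null values, 0.70 in 9.2 and 0.6 in 9.5, make this more likely to matter, because the lower null is one that ordinary prone MRI can be expected to exceed.

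**Working it through.** **Inputs.** 73 eligible patients, two-sided alpha 0.05, alternative 0.85 and null 0.70 (9.2); null 0.6 (9.5); published prone correlations 0.71, 0.75, 0.72 and 0.75 (2.1), mean 2.93/4 = 0.7325, taken as 0.73. The prone-supine correlation for objective 1 is not given, so it is varied from 0.50 to 0.95 as an assumption.

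**1. The plan's own figure.** With the Fisher transformation, power = Φ((atanh ρ₁ − atanh ρ₀)·√(n − 3) − 1.96).
For 0.85 against 0.70: (1.2562 − 0.8673) × √70 = 3.253, and Φ(3.253 − 1.96) = 90.2%. The stated 90% is reproduced.

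**2. Error rate of objective 1 under each reading.** Both scans are set at the null value with n = 73, using trivariate normal data and 200,000 replicates per setting.

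| Decision rule | False-positive rate |
|---|---|
| One named scan decides | about 5% |
| Both must be significant | at most 5% |
| Either suffices, prone-supine correlation 0.50 | 9.5% |
| Either suffices, 0.70 | 9.1% |
| Either suffices, 0.85 | 8.3% |
| Either suffices, 0.95 | 7.1% |

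The either-suffices rows use null 0.70. With null 0.6 the range is 6.8% to 9.5%. Two independent tests would give 1 − 0.95² = 9.75%. These rates count rejections in both directions, as a two-sided test does. If only a correlation above the null counted as success, the nominal level would be 2.5% per test, and either-suffices gives 4.0% to 5.2% with null 0.70.

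**3. What the standard scan does against the 0.6 null.** With a true prone correlation of 0.73: (0.9287 − 0.6931) × √70 = 1.971, and Φ(1.971 − 1.96) = 50%. Across the published values:
- 0.71: (0.8872 − 0.6931) × √70 = 1.623, giving 37%;
- 0.75: (0.9730 − 0.6931) × √70 = 2.341, giving 65%.

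**4. The two nulls on the same design.** Against 0.6, power at 0.85 is Φ(4.710 − 1.96) = 99.7%, and 37 patients would already give 90%. A scan whose true correlation is 0.70, the null in 9.2, would be declared different from 0.6 with probability Φ(1.457 − 1.96) = 31%.

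**5. Objective 2, for comparison.** For dependent correlations, z = (atanh 0.85 − atanh 0.70)·√70 / √(2 − 2c). The inter-modality correlation of 0.70 in 9.2 gives c = 0.426. Then z = 3.253/√1.149 = 3.04, and power is Φ(3.04 − 1.96) = 86%. The plan's claim of more than 80% is reproduced.

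**The case against.** The prone-only sentence in 9.1 is probably a drafting omission. The sentence before it names both scans, as do 1.2, the opening of section 9, 9.2 and 9.5. A reader might infer that the primary endpoint leaves out supine MRI. The plan as a whole does not support that, since one sentence conflicts with the rest. But it is the sentence that defines the evaluation, and restoring the missing word would still leave two tests without a rule.

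A reader might also infer that the error rate is inflated. The documents do not establish this. Alpha is stated per test, no study-wise 5% is promised, and the word or in 9.2 can mean that the power holds for each scan separately. Inflation follows only if either scan suffices, which no section says.

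Nor is it right that the plan has no powered test of supine MRI. Objective 2 is one, at about 86%. What remains is narrower: 1.2 lists three standard modalities, 9.2 and 9.5 treat the comparison as one pair of coefficients, and no section says which modality is the deciding comparator or where this test ranks.

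Finally, the published prone correlations come from patients after neoadjuvant therapy, while this trial also enrols upfront-surgery patients. The benchmark may not transfer exactly. This limits the precision of the 50% figure and means that whichever null is chosen needs a stated justification.

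**Conclusion.** The concern holds as an undefined decision rule. Sections 9.1, 9.2 and 9.5 disagree on which scan the first primary objective is tested with, and nothing settles whether prone, supine, either or both must succeed. The error rate of that objective is therefore undefined, at about 5% or less under two readings and about 7% to 9.5% under the third. The upper range rests on an assumed prone-supine correlation of 0.95 to 0.50, bivariate normal sizes, and counting rejections in both directions.

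The practical weight comes from the conflict between the nulls. Under 9.5 as written, prone MRI doing no better than published has about an even chance (37% to 65% over the cited values) of a significant primary result with no bearing on supine MRI. The sample size is not at fault: 73 patients give the stated power for one test against 0.70.

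**What to change.** 1. In 9.1, name the correlation between pre-surgical supine MRI size and pathologic size as the endpoint of objective 1, and declare it the single deciding test at two-sided 0.05.
2. State one null, with its justification, and use it in both 9.2 and 9.5. With 0.70, the stated 90% power at 73 patients is kept.
3. Estimate the prone-pathology correlation with a 95% confidence interval as the reference, without a deciding test.
4. For objective 2, name the comparator that decides (for example prone MRI) and state its place in the testing order.
5. Report the other modality comparisons and the objective 3 metrics with confidence intervals as exploratory. Objective 3 in 1.2 is already framed as exploration.
6. Align 1.2, 9.2 and 9.5 with these choices, including the reference to prone or supine in 9.2.

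**Cost.** Wording only, and no loss of power for the deciding test. The downside is that prone MRI and the lower-ranked comparisons become descriptive. If the sponsor prefers that either scan can succeed, splitting alpha at 0.025 each lowers power per test to Φ(3.253 − 2.241) = 84.4%. Restoring 90% would then need 86 evaluable patients, or 86/0.9 = 96 accrued at the plan's 10% dropout.
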